### **6.5. End of Study Definition**

A subject is considered to have completed the study if the subject has completed the Month 12 follow-up visit. The end of the study is defined as the completion of the final assessment for the last subject enrolled in the study.

### **6.6. Discontinuation of Study Treatment**

Due to the nature of the study product and dressing requirements through the Day 7 visit, discontinuation of study investigational tissue product may not be feasible unless the subject manifests an adverse reaction within 7 to 10 days of application.

### **6.7. Subject Discontinuation/Withdrawal from the Study**

Subjects are free to withdraw consent and discontinue participation in the study at any time. If a subject/parent/guardian decides to discontinue subject's participation, the reason(s) for discontinuation will be documented.

A subject's participation may be discontinued at any time at the discretion of the investigator, if the subject is uncooperative, is noncompliant, or the investigator feels that it is in the subject's best interest to be withdrawn from the study. Additionally, the subject may be considered lost to follow-up after 3 documented attempts are made to contact the subject.

All study data from withdrawn or discontinued subjects will be retained and used in the final study analyses. Subjects withdrawn or discontinued from the study may be replaced and a new subject number assigned.

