#### 5.1.3. Primary Outcome Measures:

- Percentage of participants achieving confirmed complete closure of StrataGraft treatment sites without autograft within 12 weeks of StrataGraft application, ie, percentage of participants whose burn healed after StrataGraft treatment without needing the doctor to treat the burn with skin cut from other parts of the patient's own body.
- Number of participants with treatment-emergent adverse events (TEAEs) that occurred between StrataGraft application and the end of the study (within 12 months of last data collection) and considered related to StrataGraft. This measure is not to be considered as a measure of study success.

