## 6. INVESTIGATIONAL PLAN

### 6.1. Overall Study Design

This is a prospective, open-label, single arm study to examine the safety, tolerability and clinical efficacy of StrataGraft in the treatment of DPT thermal burns in pediatric subjects. The study population will include pediatric subjects ages 2 to 17 years, inclusive, with thermal burns that contain intact dermal elements and for which autografting would be part of standard of care. As previously discussed, far more pre-school and school-aged children are burned than adolescents. Qualified subjects will be enrolled into one of two age-based cohorts: 2 to < 12 years (up to n=40) and 12 to  $\leq$  17 years (up to n=10).

Informed consent will be obtained from parents/guardians and assent from the child, when appropriate, as determined by the IRB and consistent with regulatory criteria and requirements before any protocol-related assessments or procedures are conducted. After consent is provided, data collected during the course of admission and routine assessment may be abstracted from the medical record and used for study purposes.

Following a screening period of up to 14 days, subjects will be enrolled and receive a single application of StrataGraft to 0.5% to 10% total body surface area (TBSA), which may be composed of up to 3 non-contiguous areas located on the same extremity or plane of the torso.

Subjects will return to for weekly visits until complete wound closure of all study treatment sites is confirmed. Follow-up visits will be conducted at Week 12 and Months 6 and 12. Subjects will participate in the study for approximately 13 months, not including the screening period of up to 14 days. The Schedule of Study Events is provided in [Table 2](#).

The duration of the study from first subject first visit to last subject last visit will depend upon the ability of the sites to identify and enroll eligible subjects. The study is expected to enroll subjects over a period of 12 to 18 months. The entire study is expected to require approximately 2.5 years to complete.

Safety assessments will include monitoring incidence of AEs, wound-related events, vital signs, clinical laboratory values (where possible), immunological markers (where possible), wound closure, pain, and scarring.

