To evaluate whether StrataGraft treatment eliminates or reduces the need for autografting and promotes wound closure in a pediatric population with thermal burns that contain intact dermal elements and for which autografting is clinically indicated.	All enrolled subjects who received StrataGraft	$H_0$ : The response rate of primary endpoint is less than or equal to the 50% $H_1$ : The response rate of the primary endpoint is greater than the 50%  Positive study criteria: The lower bound of primary endpoint 95% CI derived from the normal approximation to the binomial $> 50\%$ .	Percentage of subjects achieving confirmed complete closure of all StrataGraft treatment sites on or before Week 12 without autograft placement. Confirmed complete wound closure is defined as 100% re-epithelialization confirmed at 2 visits at least 2 weeks apart but before Week 20.	Early discontinuation due to: 
 
• Withdrawal of informed consent
 
• Lost to follow-up
 
• Adverse event
 
• Investigator decision
 
• Death
 
• Other
 
 Missing/incomplete data will be imputed as failure (ie, no confirmed complete wound closure).

CI = Confidence Interval; LB = Lower Bound

**Table 8: The Objective, Population, Hypotheses, Endpoints and Intercurrent Events and Data Handling for Ranked Secondary Efficacy Endpoints**

Objectives	Population	Hypotheses	Endpoints	Intercurrent events and data handling
To evaluate the mean averaged percent of wound area closure of StrataGraft treatment site without autograft placement at Week 12	All enrolled subjects who received StrataGraft	$H_{01}$ : Mean of averaged percent wound area closure of StrataGraft treatment site without autograft placement at Week 12 $\leq 50\%$ $H_{11}$ : Mean percent of wound area closure of StrataGraft treatment site without autograft placement at Week 12 $> 50\%$	Mean of averaged percent area of StrataGraft treatment site closed without autograft placement at Week 12	
Early discontinuation due to:
 
 
• Withdrawal of informed consent
 
• Lost to follow-up
 
• Adverse event
 
• Investigator decision
 
• Death
 
• Other
 
 
Missing/incomplete continuous variables will not be imputed.

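### Section 6.7 lets the investigator end a treated child's follow-up after a single application, which can flatter ranked secondary 1 and 3, the late exploratory endpoints and late adverse-event counts; the primary endpoint is protected

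*Combined protocol and SAP*

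**What the plan says.** **Treatment.** Protocol Section 6.1: "subjects will be enrolled and receive a single application of StrataGraft to 0.5% to 10% total body surface area". Section 6.6 adds that "discontinuation of study investigational tissue product may not be feasible" unless an adverse reaction appears within 7 to 10 days.

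**Leaving the study.** Section 6.7: "A subject's participation may be discontinued at any time at the discretion of the investigator, if the subject is uncooperative, is noncompliant", or if "the investigator feels that it is in the subject's best interest to be withdrawn from the study". A documented reason is required when the subject, parent or guardian decides, but the section does not ask for one when the investigator does. On data and numbers it says "All study data from withdrawn or discontinued subjects will be retained and used in the final study analyses" and "Subjects withdrawn or discontinued from the study may be replaced and a new subject number assigned". It asks for no continued follow-up, and the schedule in Table 2 has no early-termination visit.

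**Analysis.**
- Section 12.2: the ITT and Safety populations are all enrolled children who received StrataGraft.
- Sections 12.3.1.1 and 12.3.3 and Table 7: missing primary data count as failure.
- Ranked secondary 1, Table 8: "Missing/incomplete continuous variables will not be imputed".
- Ranked secondary 2: missing counts as failure in Section 12.3.1.2 and Table 8, but Section 12.3.3 says ranked secondary endpoints are not imputed.
- Ranked secondary 3, Section 12.3.1.2: autografted area is accumulated over non-missing visits up to Week 12.
- Exploratory binary endpoints, Section 12.3.1.3: not imputed.
- Tables 7 and 8 list adverse event and investigator decision among the reasons for early discontinuation.

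**Safety.** Section 5.1.3 lists "Number of participants with treatment-emergent adverse events (TEAEs) that occurred between StrataGraft application and the end of the study", where considered related to StrataGraft. Section 11.12 has events reported until the child's participation is complete; events already known are followed to resolution, stabilisation or referral to a non-study physician.

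**SAP memo.** Enrollment closed with one subject. Only listings are planned.

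**The concern.** In a trial with repeated dosing, discontinuation can mean stopping treatment while observation continues. Here nothing is left to stop after Day 1 except study procedures and observation, and Section 6.7 does not separate the two. Noncompliance with a visit schedule is no reason to stop recording whether a treated wound closed, was autografted or gave rise to an adverse event.

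The study is open-label, and under Section 11.3.2 the investigator assesses closure. The person who may end participation therefore knows how the wound is doing. If withdrawal is more likely in children who are doing badly, their outcomes are lost selectively from every endpoint without a missing-equals-failure rule.

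Section 12.3.1.2 defends the lack of imputation by expecting missing data only through loss to follow-up, because a missed visit can be made up at the next one. That does not hold for a child whose participation has been ended, which is a route that Tables 7 and 8 themselves name.

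**Working it through.** **1. The plan's own figure.** The documents give no withdrawal rate. The nearest stated figure is the power in Section 12.1: above 90% with N = 50, a null of 50% and a true rate of 83%. The smallest count whose normal-approximation 95% lower limit exceeds 50% is 32 of 50: 0.64 − 1.96 × √(0.64 × 0.36/50) = 0.507. P(X ≥ 32 | n = 50, p = 0.83) = 0.9997. For N = 40 the count is 26 and the power 0.998. The claim reproduces.

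**2. Primary endpoint.** Withdrawing a child who would not have closed changes nothing, because that child is a failure either way. Withdrawal unrelated to outcome, before confirmed closure, works against the product: 5 of 50 gives 0.83 × 45/50 = 74.7% and power 0.97; 10 of 50 gives 66.4% and power 0.70.

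**3. Ranked secondary 1.** Assumed: 50 treated; 40 fully closed at Week 12; 10 partly closed and not autografted; *k* of the 10 withdrawn before Week 12, who would have been *m*% closed; the other 10 − *k* at 60%.

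- Full follow-up: [40 × 100 + (10 − k) × 60 + k × m]/50
- As analysed: [40 × 100 + (10 − k) × 60]/(50 − k)

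For k = 4, m = 30: (4000 + 360 + 120)/50 = 89.6, against (4000 + 360)/46 = 94.8, a shift of +5.2 points.

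| k | As analysed | Shift, m = 0 | Shift, m = 30 | Shift, m = 60 |
|---|---|---|---|---|
| 2 | 93.3 | +3.7 | +2.5 | +1.3 |
| 4 | 94.8 | +7.6 | +5.2 | +2.8 |
| 6 | 96.4 | +11.6 | +8.0 | +4.4 |

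A second assumed set, with 42 closed and 8 not closed, of whom 2, 4 or 8 are withdrawn: if the 8 are at 0%, the mean moves from 84.0 to 87.5, 91.3 or 100; if they are at 50%, from 92.0 to 93.8, 95.7 or 100.

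**4. Would the test of secondary 1 change?** The null is a mean of 50% or less, tested only after the primary succeeds. In the table above the full-follow-up means run from 84.8 to 92.0, with t-based 95% lower limits from 75.3 to 87.4, so the test succeeds with or without withdrawals. In the least favourable case at N = 50 that still passes the primary (32 at 100%, 18 at 0%), the mean is 64.0 and the lower limit 50.2. At N = 40 with 26 at 100% and 14 at 0%, the lower limit is 49.6, and losing one unclosed child raises it to 51.2. With those 14 at 10% closed it is already 54.6 under full follow-up. A reversal needs that corner case.

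**5. Ranked secondary 3.** Assumed: 8 of 50 would each have 100% of their area autografted by Week 12, and 2, 4 or 8 leave before the graft. Full follow-up: 8 × 100/50 = 16%. If the departed count as zero: 12, 8 or 0%. If they are dropped: 600/48 = 12.5, 400/46 = 8.7 or 0%. The text does not say which applies; both look better than 16%.

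**6. Adverse events.** Assumed: 10 of 50 (20%) would have a first event late, and 2 or 4 of them leave beforehand. Recorded incidence is 8/50 = 16% or 6/50 = 12%. A child who leaves at Week 12 loses about 9 months of observation (Month 12 less Week 12).

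**The case against.** Much of the case on the other side stands.

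- **Safety.** The measure in Section 5.1.3 counts children. One withdrawn because of a related event has already been counted, the data are kept, and known events are still followed. Only new or later events are lost. The section also says this measure does not define study success.
- **Secondary endpoints.** A reader might infer that all the secondary results are exposed. Ranked secondary 2 is protected under Section 12.3.1.2 and Table 8, and exposed only under the conflicting sentence in Section 12.3.3.
- **Direction.** The grounds in Section 6.7 do not name complications or poor healing. Withdrawal unrelated to outcome need not bias secondary 1, and it penalises the primary.
- **Replacement.** A reader might infer that a replaced child drops out of the analysis. Section 12.2 keeps every treated child, and Section 6.7 retains the data.
- **Existing provisions.** Sections 6.1 and 11 allow remote solicitation of adverse events when a child cannot attend. This helps children still in the study, but Section 6.7 does not extend it to those taken out.
- **Best interest.** An exit in the child's best interest protects minors, and barring it would be hard to defend. The remedy need not do so.
- **Relevance.** With one subject and listings only, no secondary mean or incidence will be produced.

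What is left is that the text permits a selective loss of outcomes that is cheap to prevent.

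**Conclusion.** The point holds as a protocol-design weakness of limited reach. After a single application, ending participation at the investigator's discretion mainly ends observation. If it is linked to poor healing or complications, the estimates for ranked secondary 1 and 3 and the Month 6 and 12 exploratory endpoints can look better, and late adverse events can be missed. Under the main assumed set, secondary 1 shifts by +1.3 to +11.6 points. All withdrawal numbers, closure levels and event rates are assumptions.

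Two stronger readings are not supported. The documents do not show that investigators would withdraw children who do badly, so the results can be biased, not that they are. Nor is the study's success in doubt: the primary counts missing as failure, and the test of secondary 1 against 50% would change only in a corner case. Under the SAP memo no formal result is affected now; the point matters if the protocol is resumed or reused.

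**What to change.** In Section 6.7, state that after StrataGraft application the investigator may stop study procedures, including in the child's best interest, but that this does not by itself end follow-up. Unless consent or assent is withdrawn, or the child is lost to follow-up or dies:

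- keep collecting adverse events to Month 12 and autograft status, by telephone, video or chart;
- record Week 12 wound status where the child is seen in person, since Section 11 allows closure to be assessed only face-to-face.

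Require a documented reason for every investigator discontinuation. Bring Section 12.3.3 into line with Section 12.3.1.2 and Table 8 on ranked secondary 2. Keep adverse event and investigator decision in Tables 7 and 8: they name events that can still occur, and removing them would take those events out of the missing-data rows without preventing them.

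The cost is protocol wording and a little extra site follow-up for a few children. Clinical care and the right to withdraw are untouched.

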## 6.8. Schedule of Study Events and Assessments

Table 2: Schedule of Study Events and Assessments

	Screening Days -14 to -1	Day 1 (Baseline)	Day 7 ± 2 days	Day 14 ± 2 days	Day 21 ± 2 days	Day 28 ± 3 days	Weeks 5, 6, 7, etc a ± 3 days	Week 12 ± 1 week / Months 6 & 12 (± 4 weeks )
Informed consent/assent b	✓							
Medical history and limited physical examination o	✓							
Pregnancy test c	✓							
Vital signs	✓	✓	✓	✓	✓	✓	✓	✓
Height and weight	✓							✓
Safety laboratory tests (CMP and CBC) d		✓					✓	
StrataGraft application		✓						
Treatment site assessment n		✓	✓	✓	✓	✓	✓	✓
Wound closure assessment j			✓ j	✓ j	✓ j	✓ j	✓ j	✓ j
Pain assessment (EVENDOL or FPRS) k			✓	✓	✓	✓	✓	✓
Assessment of need for continued hospitalization l			✓	✓	✓	✓	✓	✓
Photograph treatment sites		✓ e	✓ f	✓ f	✓ f	✓ f	✓ f	✓ f
Skin quality assessment (POSAS)				✓ g	✓ g	✓ g	✓ g	✓ g

	Screening Days -14 to -1	Day 1 (Baseline)	Day 7 ± 2 days	Day 14 ± 2 days	Day 21 ± 2 days	Day 28 ± 3 days	Weeks 5, 6, 7, etc a ± 3 days	Week 12 ± 1 week / Months 6 & 12 (± 4 weeks )
Satisfaction with scar (PSAQ)				✓ g	✓ g	✓ g	✓ g	✓ g
Concomitant medications and procedures m	✓	✓	✓	✓	✓	✓	✓	✓
Immunological samples h (PRA & anti-BSA)		✓ h					✓ h	✓ h
Archival samples i		✓						
Adverse event monitoring	✓	✓	✓	✓	✓	✓	✓	✓

a Assessed weekly until wound confirmed as completely closed at a second visit at least 2 weeks after initial observation of closure but no later than Week 20, then assessed at Week 12 and Months 6 and 12.

b For purposes of this study, parents/legal guardians will consent on behalf of the child but assent from the child will also be solicited, when appropriate, as determined by the Institutional Review Board (IRB), consistent with regulatory criteria and requirements. Subjects who reach 18 years of age during their participation in the study will be re-consented.

c Females of childbearing potential only.

d Safety laboratory results will be collected prior to StrataGraft application and abstracted from the medical record, if available. If such results are not available, blood samples for study purposes will be collected as part of a clinically necessary venipuncture. A second safety laboratory assessment will be performed between Study Day 28 and Study Week 11, with results abstracted from the medical record, if available, or collected as part of a clinically necessary venipuncture.

e During the excision/debridement procedure, photographs will be taken of the study site(s) 1) pre-excision/debridement, 2) post-excision/debridement, and 3) post-StrataGraft application.

f Photograph all study treatment site(s) until complete closure, Week 12, or until the study burn is autografted; then photograph at Months 6 and 12. Photographs may be taken by trained caregivers or by study site personnel.

g Conducted at the first observation of closure, Week 12 (if closed prior), and Months 6 and 12.

h Immunological samples (monitoring of PRA and anti-BSA antibodies) will be collected prior to StrataGraft application, and one time again between Week 6 and Month 6 for all treated subjects

i Archival blood samples will be collected before application of StrataGraft and shipped for long-term storage.

j Wounds will be assessed for percent re-epithelialization at least weekly, beginning at the Day 7 visit, until complete wound closure is confirmed. Confirmation of closure will occur at least 2 weeks after initial observation of wound closure but no later than Week 20. Maintenance of closure will be assessed at each subsequent study visit following confirmation of wound closure.

k Assess pain only if wound is open.

 Note reason(s) for continued hospitalization such as pain management, fluid or nutritional status, infection risk, ongoing infection, inability to perform activities of daily living, insufficient social support, or other issues.

m Start/stop date, dose, unit, frequency, route and indication for all prior (taken within the 14 days prior to Day 1) and concomitant medications (taken from Screening through the Month 12 end of study visit) and nondrug therapies (eg, blood transfusions, oxygen supplementation, physical therapy, etc) administered will be recorded.

n Treatment site evaluations include assessment for signs & symptoms of infection or other adverse events and application of autograft.

o Medical history to include significant past morbidities, surgical procedures, etc. Limited physical exam will include review of systems and assessment of burn area, depth and location(s).

Anti-BSA = antibodies to bovine serum albumin; CMP = comprehensive metabolic panel; CBC = complete blood count w/ differential; EVENDOL = EValuation ENfant DOuLeur; FPRS = Wong-Baker Faces Pain Rating Scale; POSAS = Patient and Observer Scar Assessment Scale; PRA = panel reactive antibodies; PSAQ = Patient Scar Assessment Questionnaire.

## 7. SELECTION AND WITHDRAWAL OF SUBJECTS

In this study, up to 50 subjects will be enrolled into one of two age cohorts: 2 to < 12 years (up to n = 40) and 12 to ≤ 17 years (up to n = 10). Subjects who fail to meet eligibility criteria following excision/debridement of their wound but before StrataGraft application may be replaced and a new subject number assigned.

### 7.1. Subject Inclusion Criteria

An included subject will be or have:

1. Aged 2 to 17 years, inclusive, as of the time of consent.
2. Written informed consent from parent(s) or legal guardian(s) and assent from the child when appropriate, as determined by the Institutional Review Board (IRB), consistent with regulatory criteria and requirements.
3. Sufficient healthy skin identified and reserved as a donor site in the event that the StrataGraft treatment site(s) requires autografting.
4. Thermal burns of no more than 30% TBSA.
5. Consenting adult(s) is/are able and willing to attend/bring child to the scheduled visits and comply with study procedures.
6. Study treatment area(s) that is/are: a) DPT in depth (ie, containing dermal elements) and for which excision and autografting are clinically indicated, as assessed by the investigator, and b) located on the torso or extremities.
7. Study treatment area of 0.5% to 10% TBSA, which may be composed of up to 3 non-contiguous areas located on the same extremity or plane of the torso.

### 7.2. Subject Exclusion Criteria

An excluded subject will be or have:

1. Pregnant or breastfeeding.
2. Receiving systemic immunosuppressive therapy and/or systemic corticosteroids (inhaled corticosteroids are allowed)
3. A known history of malignancy.
4. Pre-admission insulin-dependent diabetes.
5. Concurrent trauma, conditions, and/or personal situations that, in the opinion of the investigator, may compromise subject safety or the study objectives.
6. Burn injury occurred ≥ 14 days prior to StrataGraft application.
7. An expected survival of less than 12 months.
8. Participated in an interventional study of a drug, device, or biologic within the 90 days preceding enrollment.
9. Proposed study site(s) has/have been previously excised and/or autografted.

10. Proposed study site(s) are located adjacent to an unexcised burn area.
11. Proposed study site(s) demonstrate signs and symptoms of wound infection, per judgment of the clinical investigator.
12. Proposed study sites(s) lie across joints or are located on the feet (ie, distal to the malleolus), hands (distal to the wrist), face, neck, buttocks, perineum, or genitalia.

